11.4.2 Laboratory Tests

Laboratory values will be summarized by treatment group, including changes from baseline at each time point. The number (percentage) of subject with abnormal will be summarized and the shift tables will be tabulated by treatment group and time points.

11.4.3 Vital Signs

Vital sign measurements will be summarized by treatment group, including changes from baseline at each time point.

11.4.4 Electrocardiograms

ECGs will be summarized by treatment group, including changes from baseline at each time point.

11.4.5 Cystoscopy

The number (percentage) of subjects with abnormal cystoscopy will be summarized by treatment group.

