8.2.2 Cystoscopy

- Assessment Points: Cystoscopy will be performed on Day 1 (pre-dose) to identify presence or absence of Hunner's lesion as well as Day 8, and Day 29 or an early withdrawal visit to evaluate abnormal change from Day 1.
- Method: Subjects must fully void their bladders after the cystoscopy procedure in preparation for the IP instillation. About five photographs inside the bladder will be printed and filed with each subject's source document.

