11.6.1 Visit Window and Unscheduled Assessments

The data collected during follow-up time point will be displayed and analyzed according to the actual visit date in the eCRF. Assessments taken outside of protocol-allowable windows will be displayed according to the eCRF assessment recorded by the Investigator.

Unscheduled assessments (laboratory data or vital signs associated with non-protocol clinical visits or obtained in investigating or managing AEs) will be included in listings but not summaries of the data.

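### The planned cystoscopy summary (Section 11.4.5) has no Day 1 reference, although Section 8.2.2 does the post-dose cystoscopies to look for change from Day 1

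*Combined protocol and SAP*

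**What the plan says.** Section 8.2.2 schedules three cystoscopies and gives two purposes. Before dosing, "Cystoscopy will be performed on Day 1 (pre-dose) to identify presence or absence of Hunner's lesion". After dosing, it is repeated on "Day 8, and Day 29 or an early withdrawal visit to evaluate abnormal change from Day 1". The same section has about five photographs of the bladder interior printed and filed for each subject.

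The whole planned analysis is in Section 11.4.5: "The number (percentage) of subjects with abnormal cystoscopy will be summarized by treatment group". It names no visit, Day 1 status, change or shift, and it does not define an abnormal cystoscopy. The synopsis says only that cystoscopy will be summarized by treatment group.

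The three preceding sections all refer to baseline:

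- Laboratory tests (11.4.2) have changes from baseline, and "the shift tables will be tabulated by treatment group and time points".
- Vital signs (11.4.3): "Vital sign measurements will be summarized by treatment group, including changes from baseline at each time point".
- Electrocardiograms (11.4.4): "ECGs will be summarized by treatment group, including changes from baseline at each time point".

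Two general rules in Section 11.6.1 also bear on the point. One may lead to a display by visit: "The data collected during follow-up time point will be displayed and analyzed according to the actual visit date in the eCRF". The other keeps unscheduled assessments out of the summaries, but its parenthesis covers only laboratory data and vital signs: "Unscheduled assessments (laboratory data or vital signs associated with non-protocol clinical visits". Section 9.10 allows cystoscopy at an unscheduled visit.

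**The concern.** Safety and tolerability is a primary objective, the product is instilled into the bladder, and cystoscopy is the only assessment that looks directly at that organ. Section 8.2.2 asks whether the bladder changed after dosing. Section 11.4.5 reports how many subjects have an abnormal bladder, which is a different quantity whenever some subjects are abnormal before dosing. The protocol foresees such subjects: the Day 1 examination records Hunner's lesion, and Section 4.2 does not exclude it.

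With 6 subjects per dose group and 8 on pooled placebo, one or two subjects with old lesions could make a group look affected, and one or two with new findings could pass as background. A reader who wants change from Day 1 would have to rebuild it from listings or rely on which findings the investigators reported as adverse events.

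**Working it through.** The plan gives no figure for this point, so there is none to reproduce. The check asks how much the planned count can say about change from Day 1.

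**Inputs.** Four cohorts at 6:2 (Sections 3.2 and 3.5) give 4 × 6 = 24 on SI-722 and 4 × 2 = 8 on placebo, which agrees with the total of 32 in Section 3.4. Section 11.6 pools placebo. The group sizes are therefore n = 6 per dose and n = 8 for placebo.

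**Case 1: one count, with no split by visit.** If k of n subjects are reported abnormal, the number with a new or worsened finding can be anything from 0 (all were present on Day 1 and unchanged) to k.

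**Case 2: counts by visit.** Let a be the number abnormal on Day 1 and b the number abnormal at one post-dose visit. Each subject is normal at both, newly abnormal, resolved, abnormal at both and not worse, or abnormal at both and worse.

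- Minimum new or worsened: at most a of the b post-dose abnormals can be old and unchanged, so at least max(0, b − a) are new.
- Maximum new or worsened: all b can be new findings or worsened old ones, so the maximum is b.
- Width of the range: b − max(0, b − a) = min(a, b). The number is settled only if a = 0 or b = 0.

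| Group | Day 1 | Post-dose | New or worsened | As a percentage |
|---|---|---|---|---|
| Dose, n = 6 | 2/6 | 2/6 | 0 to 2 | 0% to 33.3% |
| Dose, n = 6 | 3/6 | 3/6 | 0 to 3 | 0% to 50% |
| Dose, n = 6 | 2/6 | 3/6 | 1 to 3 | 16.7% to 50% |
| Dose, n = 6 | 0/6 | 3/6 | 3 | 50% |
| Placebo, n = 8 | 2/8 | 2/8 | 0 to 2 | 0% to 25% |

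In the first row, the two abnormal subjects may be the same people, unchanged (0). They may be the same people, both worse (2). Or two may have resolved while two others became abnormal (2).

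**How often the pair of counts leaves the answer open.** For n = 6 there are 7 × 7 = 49 possible pairs, and a and b are both at least 1 in 6 × 6 = 36 of them. For n = 8 the figures are 8 × 8 = 64 of 9 × 9 = 81. If only newly abnormal subjects are wanted, the range is max(0, b − a) to min(b, n − a). It is then open when a and b both lie between 1 and n − 1, which is 5 × 5 = 25 of 49 and 7 × 7 = 49 of 81. These are counts of possible tables, not probabilities.

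**Whether a > 0 is likely.** The documents give no Day 1 rate of abnormal cystoscopy, so this is an assumption. With rate q, the chance that a dose group of 6 has at least one subject abnormal before dosing is 1 − (1 − q)^6:

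- q = 10%: 1 − 0.9^6 = 47%
- q = 20%: 1 − 0.8^6 = 74%
- q = 30%: 1 − 0.7^6 = 88%
- q = 50%: 1 − 0.5^6 = 98%

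**The case against.** **The SAP.** Section 11 says it describes key analyses and leaves additional analyses and data handling to an SAP. No SAP text on cystoscopy was available, so a Day 1 comparison may already be planned. This stands as a limit on certainty. However, the protocol states the baseline reference for laboratory, vital-sign and ECG data without waiting for the SAP.

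**The meaning of abnormal.** If post-dose results are recorded as abnormal change from Day 1, as Section 8.2.2 could suggest, the count in 11.4.5 is already a count of change. The ranges above would then not apply, and only an undefined term would remain. That reading is possible, but 11.4.5 does not state it.

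**Adverse event tables.** Section 10.1 names cystoscopy findings as a source of adverse events, Appendix 12 includes new and exacerbated conditions, and Section 11.4.1 tabulates treatment-emergent events by group. Findings that are treated or judged important therefore do reach a change-based summary. This cover is real but partial. Under 10.3, entry depends on treatment or on the investigator's judgement. Appendix 12 also leaves out abnormal assessments associated with the underlying disease unless they are judged more severe than expected, and in a bladder disease that filter falls on bladder findings themselves.

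**Consequence.** The summary is descriptive, no dose decision is tied to it, and listings for 32 subjects can be read by hand. That limits the seriousness, but it does not supply the missing summary.

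**Comparators.** Vital signs and ECG intervals are numeric, so change from baseline is routine there. The laboratory shift tables are the closer precedent, and they are enough to show that the plan uses this method for categorical status.

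**Conclusion.** The concern holds. As written, the only planned cystoscopy summary does not report change from Day 1, which is what Section 8.2.2 says the post-dose examinations are for. Counts by visit would not repair this: whenever at least one subject is abnormal on Day 1 and at least one post-dose, the number new or worsened is uncertain by min(a, b) subjects, and each subject is 16.7 percentage points of a dose group.

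The conclusion rests on reading abnormal in its ordinary sense, as status at the examination, and on the protocol text alone. The size in practice depends on how many subjects are abnormal before dosing, which the documents do not give. This is a gap in the planned summary, not a loss of data. It should be corrected, with medium confidence because the SAP may already do so.

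**What to change.** In Section 11.4.5 or the SAP, replace the plain count with shift tables of cystoscopy status from Day 1 to Day 8 and from Day 1 to Day 29 or early withdrawal, by treatment group. Give the number and percentage of subjects with a new or worsened finding since Day 1 as the main count.

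Two clarifications belong with it. Define an abnormal cystoscopy. State whether unscheduled cystoscopies (Section 9.10) enter the count, since the parenthesis in 11.6.1 mentions only laboratory data and vital signs.

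The cost is one extra table and one or two sentences, using examinations and photographs already planned. The drawback is that new or worsened needs an investigator's judgement against the Day 1 record and photographs. If the SAP already contains this, a cross-reference in 11.4.5 is enough.

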11.5 Efficacy Analyses

All efficacy analysis will be conducted based on the ITT population.

Each efficacy assessment will be summarized for all subjects by treatment group at each assessment visit. The assessments collected on daily diary will be calculated by average at each assessment visit. Efficacy assessments from the daily diary such as bladder pain and symptoms of IC/BPS will be summarized by study day in addition to the summary at each assessment visit.

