8.3 Efficacy Assessments

8.3.1 Daily Diary

8.3.1.1 Bladder Pain

- Assessment Points: Daily from Day -7 until Day 29. Bladder pain assessment must be taken at least 5 days in a week prior to Day 1.
- Item: Daily bladder pain score using a standardized 11-points numerical rating scale (NRS) pain scale in subject daily diary (See [Appendix 2](#)).
- Method: Subjects will record daily maximum and average bladder pain over the last 24 hours and bladder pain at that time, basically before going to bed.

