8.3.1.3 Voiding Frequency

- Assessment Points: Daily from Day -7 until Day 29. This assessment must be taken at least 5 days in a week prior to Day 1.
- Item: See [Appendix 4](#)
- Method: Subjects will record the number of times of the diurnal (from the time of getting up to the time of going to bed) and nocturnal (overnight) urination.

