8.3.1.5 Voiding Volume

- Assessment Points: One day within 7 days before Day 1, within 3 days before or after Day 8 and Day 15, and within 5 days before Day 29.
- Item: See [Appendix 6](#)
- Method: Subjects will measure voiding volume at least 5 times in a day preferably including the first and last urine.

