8.3.2 Patient Reported Outcomes at the Study Site

8.3.2.1 Interstitial Cystitis Symptom Index Score/Problem Index

- Assessment Points: Day 1 (pre-dose) and Day 29 or an early withdrawal visit.
- Item: See [Appendix 8](#)
- Method: The Interstitial Cystitis Symptom Index/Problem Index (ICSI/PI) questionnaire will be administered to the subjects at each listed visit.

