8.3.2.2 Bladder Pain/Interstitial Cystitis Symptom Score

- Assessment Points: Screening, Day 1 (pre-dose), Day 8, Day 15 and Day 29 or an early withdrawal visit.
- Item: See [Appendix 9](#)
- Method: The BPIC-SS questionnaire will be administered to the subjects at each listed visit.

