11.6.3 Missing Data

Missing data will not be imputed and will be excluded from the analysis.

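### Apart from ESR/CRP and the GRA, section 11.5 plans only raw efficacy summaries, with no change from baseline or baseline adjustment, although pre-dose values are collected and missing values are excluded

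*Combined protocol and SAP*

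**What the plan says.** Section 11.5, repeated in the synopsis, uses the ITT population and states: "Each efficacy assessment will be summarized for all subjects by treatment group at each assessment visit". Diary items are averaged for each visit and also shown by study day. Section 11.6 adds generic descriptive statistics and pools placebo. Section 11.6.3 states: "Missing data will not be imputed and will be excluded from the analysis".

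Pre-dose values exist for most efficacy measures:

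- Bladder pain NRS (8.3.1.1): "Bladder pain assessment must be taken at least 5 days in a week prior to Day 1". Voiding frequency (8.3.1.3) carries the same rule: "This assessment must be taken at least 5 days in a week prior to Day 1". Acetaminophen use (8.3.1.6) is recorded from Day -7.
- Voiding volume (8.3.1.5): "One day within 7 days before Day 1".
- ICSI/PI (8.3.2.1): "Day 1 (pre-dose) and Day 29 or an early withdrawal visit".
- BPIC-SS (8.3.2.2): "Screening, Day 1 (pre-dose), Day 8, Day 15 and Day 29 or an early withdrawal visit".

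The safety sections do name change. Section 11.4.2 reads: "Laboratory values will be summarized by treatment group, including changes from baseline at each time point". Sections 11.4.3 and 11.4.4 do the same for vital signs and ECGs. Section 11 says that key analyses are given there and leaves additional analyses and data-handling details to a SAP. No separate SAP text is in the supplied document.

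**The concern.** Preliminary efficacy is the only secondary objective, and each dose will naturally be read against pooled placebo. Raw means by visit are a weak basis for that, for three reasons.

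- When values are missing, the baseline and follow-up means need not describe the same people, so their difference need not be the mean within-subject change.
- The SD of individual change cannot be recovered from the SDs at two visits.
- With six subjects per dose, groups will often differ before dosing by chance, and nothing in 11.5 allows for this.

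The choice of baseline also matters for BPIC-SS. It is measured at Screening and again on Day 1, and section 18.2 can add a repeat. Section 4.1 requires a Screening score of 19 or more, so the Screening value is a selected one, and change measured from it may include regression to the mean.

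**Working it through.** **The plan's own figure.** Sections 3.4 and 3.5: 4 cohorts × (6 + 2) = 32, that is 24 + 8. This reproduces. The supplied text gives no SD, effect size or baseline-to-follow-up correlation (rho). Results below are therefore in SD units, and rho is an assumption shown over a range.

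**1. Text check: is change from baseline planned?**

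| Measure | Pre-dose value | Change planned in supplied text |
|---|---|---|
| Bladder pain NRS, voiding frequency, acetaminophen | Diary from Day -7 | No |
| Voiding volume | One day in the week before Day 1 | No |
| BPIC-SS | Screening and Day 1 | No |
| ICSI/PI | Day 1 | No |
| ESR, CRP | Screening and Day 1 (8.3.4) | Yes, as laboratory values (11.4.2, Table 4) |
| GRA | None | Self-rated change (Appendix 10) |

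**2. Different subjects at different visits.** The number missing is an assumption. If 1 of 6 is missing at follow-up, the difference in visit means departs from the mean change of the other five by (missing subject's baseline − mean baseline of the other five)/6.

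- Gap of 1 SD: 1/6 = 0.17 SD. Gap of 2 SD: 2/6 = 0.33 SD.
- With 2 of 6 missing, the factor is 2/6, or 0.33 SD per 1 SD gap between the two missing and the four remaining.
- If missingness is unrelated to the score, the shift averages zero. Its SD is √[(1/36)(1 + 1/5)] = 0.18 for one missing and √[(1/9)(1/2 + 1/4)] = 0.29 for two.
- An extreme example: baseline NRS 4, 5, 5, 6, 6, 10, the last subject missing later, the rest unchanged. The means are 36/6 = 6.0 and 26/5 = 5.2, an apparent fall of 0.8, while mean paired change is 0. The missing subject lies 4.8 points from the others' mean, about 2.3 sample SDs (SD = √(22/5) = 2.1).

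**3. Chance baseline differences.** One dose against pooled placebo: SE = √(1/6 + 1/8) = 0.540 SD.

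- Above 0.5 SD: 2[1 − Φ(0.5/0.540)] = 0.355. Above 1.0 SD: 2[1 − Φ(1.0/0.540)] = 0.064.
- At least one of four doses against the shared placebo group (1,000,000 simulated trials): 0.779 and 0.204.
- All active against placebo (24 vs 8): SE 0.408; 0.221 and 0.014.

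These figures assume normal scores and that subjects from different cohorts are exchangeable.

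**4. SD of change.** √[2(1 − rho)] = 1.18, 1.00 and 0.77 SD at rho 0.3, 0.5 and 0.7.

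**5. Precision of a dose-minus-placebo contrast.** Mean 95% CI half-width in SD from one five-group model (6, 6, 6, 6, 8), 20,000 simulated trials per rho; raw and change use 27 df, ANCOVA 26.

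| rho | Raw | Change score | ANCOVA | ANCOVA vs raw |
|---|---|---|---|---|
| 0 | 1.10 | 1.55 | 1.12 | 2% wider |
| 0.3 | 1.10 | 1.30 | 1.07 | 3% narrower |
| 0.5 | 1.10 | 1.10 | 0.97 | 12% narrower |
| 0.7 | 1.10 | 0.85 | 0.80 | 27% narrower |

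With one missing per group, raw is 1.20 and ANCOVA 1.23, 1.18, 1.07 and 0.88. A two-group model using only the 6 and the 8 gives about 1.18 raw and 1.19 ANCOVA at rho 0.3, so no gain there. At low rho a change-score contrast is wider than the raw one. Change therefore suits description, and ANCOVA suits the contrast.

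**The case against.** The other side has a substantial case.

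- **The SAP may cover it.** Section 11 defers details, and baseline is not defined for laboratory values or vital signs either, although both have Screening and Day 1 values. That suggests definitions were left to the SAP generally. This stands as a limit: the finding concerns the supplied text only.
- **Change is partly planned.** ESR and CRP are covered by 11.4.2, and the GRA describes individual response. Both stand. The GRA is a retrospective rating with no pre-dose value, so it does not replace change in the scored measures.
- **Baseline is mostly obvious.** ICSI/PI and voiding volume each have a single pre-dose occasion, and the diary has a defined week. This largely stands; the real choice is BPIC-SS.
- **Missing data are limited and visible.** The early-withdrawal visit (9.9) and telephone collection (18.3) capture BPIC-SS, ICSI/PI and GRA, and section 11.6 reports n. This reduces the problem, but those provisions are for the questionnaires and do not supply later diary days. A visible n does not give the paired change.
- **Descriptive analysis is defensible here.** For a preliminary objective with 32 subjects, it is. The main request is itself descriptive. The ANCOVA gain rests on an unknown rho and is small or nil at 0.3, so it belongs as a supplement.
- **Placebo is pooled across cohorts filled in sequence.** Six of the eight placebo subjects come from cohorts other than the dose being compared. Adjusting for baseline does not remove differences between cohorts.

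**Conclusion.** The point holds for the supplied text. Outside ESR/CRP and the GRA, efficacy is planned as raw summaries, without change from baseline or a baseline-adjusted contrast. Followed as written, the plan can show a shift in means when no subject changed: 0.17 SD for one of six missing at a 1 SD gap, and more in extreme cases. Chance baseline differences above 0.5 SD are likely in at least one dose group (78%).

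A reader might infer more than this, and the documents do not support it.

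- They do not show that the sponsor never planned change from baseline, because the SAP text is not supplied.
- They do not show that the efficacy comparison is biased. Chance imbalance within randomized groups is imprecision, and whether pooling across cohorts adds bias cannot be judged from the text.
- They do not show that a formal efficacy test is required. Section 11.6.2 sets a 5% level and 95% intervals, but section 11 attaches them to no efficacy endpoint.

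Paired change corrects the mismatch of subjects between visits; it does not correct selective dropout. Intervals stay wide under any method. The SD-based figures assume normal scores and do not apply to the four-level diary items. The primary PK and safety objectives are unaffected, and no data are lost. This is a minor-to-moderate improvement, best settled before unblinding.

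**What to change.** In section 11.5, or by citing the SAP if it already does this:

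1. Define baseline as the mean of available Day -7 to Day -1 diary values for bladder pain NRS, voiding frequency and acetaminophen use; the Day 1 pre-dose score for BPIC-SS (not the Screening score used for eligibility) and ICSI/PI; and the single pre-dose measurement day for voiding volume.
2. Add descriptive change from baseline (n, mean, SD, median, min, max) for these measures in subjects with both values. Leave the GRA and the four-level diary items as planned.
3. As an exploratory supplement, name one or two measures and one visit (for example average bladder pain NRS and BPIC-SS at Day 29). Report each dose minus pooled placebo with a 95% CI from one five-group ANCOVA with baseline as covariate, at most 4 × 2 = 8 intervals. State that there is no multiplicity control, that placebo is pooled across sequentially filled cohorts, and that the precision gain depends on an unknown correlation.

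The cost is a few sentences, with no new data, visits or subjects. The ANCOVA uses one degree of freedom, and its intervals are about 2% wider if rho is near 0 (about 3% with one subject missing per group).

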11.6 General Considerations

Placebo group will be combined regardless of planned volume. All study-collected data will be summarized by treatment group using descriptive statistics, graphs, and/or data listings. Unless otherwise specified, descriptive statistics for continuous variables will include number of subjects (n), mean, standard deviation (SD), median, and minimum (min) and maximum (max) values, and analysis of categorical variables will include number of patients (n) and percentage.

11.6.1 Visit Window and Unscheduled Assessments

The data collected during follow-up time point will be displayed and analyzed according to the actual visit date in the eCRF. Assessments taken outside of protocol-allowable windows will be displayed according to the eCRF assessment recorded by the Investigator.

Unscheduled assessments (laboratory data or vital signs associated with non-protocol clinical visits or obtained in investigating or managing AEs) will be included in listings but not summaries of the data.

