2 OBJECTIVES

Primary Objectives:

- To provide the PK profiles of single intravesical instillations of SI-722 in IC/BPS subjects
- To assess the safety and tolerability of single intravesical instillations of SI-722 in IC/BPS subjects

Secondary Objective:

- To assess the preliminary efficacy of single intravesical instillations of SI-722 in IC/BPS subjects

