8.2.6 Clinical Laboratory Assessments

- Assessment Points: Blood and urine samples for clinical laboratory tests (blood: hematology, coagulation and clinical chemistry, urine: urinalysis) will be collected at Screening, pre-dose on Day 1, Day 2, Day 3, Day 5, Day 8, Day 15 and Day 29 or early withdrawal.

Serology (HIV antibodies, HBsAg, and HCV antibody), TB blood test, Nucleic acid amplification testing (NAAT) for *Neisseria. gonorrhoeae* and *Chlamydia. trachomatis* and Urine drug screen will be done at Screening only.

Pregnancy tests will be done at Screening (serum), pre-dose on Day 1 (urine), and on Day 29 or early withdrawal (urine). Urine culture will be done at Screening, and on Day 29 or early withdrawal.

- Method: The Investigator must review the laboratory report, document this review, and record any clinically relevant changes occurring during the study in the AE section in the eCRF. The laboratory reports must be filed with the source documents. All laboratory tests with values considered clinically significantly abnormal during participation in the study should be repeated until the values return to normal or baseline, or are no longer considered clinically significant by the Investigator, or are otherwise explained and any appropriate action taken.
 - If such values do not return to normal/baseline within a period of time judged reasonable by the Investigator, the etiology should be identified and the Sponsor notified.

- All protocol-required laboratory assessments, as defined in [Appendix 1](#), must be conducted in accordance with the laboratory manual and the Schedule of Activities (see [Table 1](#)).
- If laboratory values from non-protocol specified laboratory assessments performed at the institution's local laboratory require a change in subject management or are considered clinically significant by the Investigator (eg, serious AE [SAE], AE, or dose modification), then the results must be recorded in the eCRF.

Immediate safety concerns should be discussed with the medical monitor upon occurrence or awareness to determine if the subject should discontinue study treatment (See [Appendix 1](#)).

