9.10 Unscheduled Visit

In the event the Investigator needs to conduct follow-up assessments to evaluate an AE, the following safety assessments may be performed on an unscheduled visit:

- Physical examination
- Record vital signs
- Collect blood sample for laboratory tests (hematology and chemistry) and PK if considered appropriate
- Perform cystoscopy, if necessary

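### Laboratory abnormalities seen only at AE-prompted draws drop out of the abnormality counts and shift tables: unscheduled values go to listings only, and no worst-post-dose table is planned

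*Combined protocol and SAP*

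**What the plan says.** Safety is one of the two primary objectives in Section 2: "To assess the safety and tolerability of single intravesical instillations of SI-722 in IC/BPS subjects".

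Section 8.2.6 fixes the laboratory schedule. Blood and urine samples "will be collected at Screening, pre-dose on Day 1, Day 2, Day 3, Day 5, Day 8, Day 15 and Day 29 or early withdrawal". The same section says that clinically significant abnormal values "should be repeated until the values return to normal or baseline", or until they are no longer significant or are otherwise explained. Section 9.10 adds a second source of extra values: "In the event the Investigator needs to conduct follow-up assessments to evaluate an AE, the following safety assessments may be performed on an unscheduled visit". Hematology and chemistry are among those assessments.

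Section 11.4.2 gives the laboratory analysis: "The number (percentage) of subject with abnormal will be summarized and the shift tables will be tabulated by treatment group and time points". Section 11.6.1 then deals with unscheduled laboratory data and vital signs. Those from non-protocol visits, or "obtained in investigating or managing AEs) will be included in listings but not summaries of the data". It states no exception for abnormality counts or shift tables.

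**The concern.** Leaving unscheduled values out of by-visit means is ordinary practice. The difficulty is that the same rule, without an exception, also governs the tables meant to show who became abnormal. Those tables run by scheduled time point, so an AE-prompted value has no row to enter, and no any-time or worst-value table picks it up.

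The values left out are not a random subset, because many exist only because something went wrong. For a count of subjects ever abnormal, leaving values out can only lower the count or leave it unchanged. The loss would tend to be larger in groups with more events. In an ascending-dose study with six active subjects per cohort, that could soften a dose-related laboratory pattern.

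**Working it through.** **The plan's own figure.** Section 3.5 randomizes 6:2 within four cohorts, so 4 × (6 + 2) = 32, with 4 × 6 = 24 on SI-722 and 4 × 2 = 8 on placebo. This reproduces Section 3.4. Section 11.6 pools placebo, so the denominators are 6 per dose group and 8 for placebo, if all are dosed.

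**Tracing a value through the rules.** Two hypothetical subjects show what is and is not lost.

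- *Subject A* is in range at every scheduled draw, has an unscheduled visit on Day 11 to evaluate an AE, and is abnormal on that draw. Section 11.6.1 sends the Day 11 value to listings. Section 11.4.2 shows normal at Day 8 and at Day 15. No laboratory summary counts Subject A as abnormal.
- *Subject B* is abnormal at the scheduled Day 8 draw, is higher at a repeat on Day 10, and is normal by Day 15. Subject B is counted at Day 8. Only the higher peak is lost.

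A wholly uncounted subject therefore needs a first abnormality at an unscheduled draw and in-range values at every scheduled one.

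**Where this can happen.** Draws on Days 1 (pre-dose), 2, 3, 5, 8, 15 and 29 leave gaps of 1, 1, 2, 3, 7 and 14 days. Early coverage is dense, and the exposure lies in the last two gaps. With the visit windows in the headings of Sections 9.6 to 9.8 (Day 8 ± 3, Day 15 ± 3, Day 29 ± 5), these can stretch to 18 − 5 = 13 days and 34 − 12 = 22 days.

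**Size per uncounted subject.**

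- Dose group: 1/6 = 16.7 percentage points.
- Pooled placebo: 1/8 = 12.5 points.
- All SI-722 subjects: 1/24 = 4.2 points.

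A dose group shown as 0/6 (exact 95% interval 0 to 45.9%) would become 1/6 (0.4% to 64.1%).

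**How often.** The documents give no rate for subjects abnormal only at an unscheduled draw. Call it q, an assumption. The chance of at least one such subject among n is 1 − (1 − q)^n.

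| Assumed q | n = 6 | n = 32 |
|---|---|---|
| 2% | 11% | 48% |
| 5% | 27% | 81% |
| 10% | 47% | 97% |
| 15% | 62% | 99% |

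The table shows only how the chance depends on q. It does not estimate how often this will occur.

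**The case against.** The strongest reply is that little is actually hidden. An unscheduled visit under Section 9.10 is held to evaluate an AE, so the event behind it should already be in the TEAE tables of Section 11.4.1. Section 8.2.6 also has the Investigator enter clinically relevant laboratory changes as AEs, and Section 10.1 requires AEs to be documented whatever their source. Every value stays in the listings, which are readable with six subjects per dose group. Repeats usually follow a scheduled value already counted. The missing piece is an extra table, and Section 11 defers data-handling details to a SAP that could contain it.

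Most of this stands, and it limits the point. It does not remove it. Whether an abnormal result becomes an AE is left to Investigator judgement in Section 10.3, and Appendix 12 excludes findings associated with the underlying disease unless they are more severe than expected. TEAE tables give term, severity and relationship, but neither the value nor its shift from baseline. Listings give no group counts. No exception to Section 11.6.1 appears in the text supplied.

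A reader might infer that the same fault affects vital signs and cystoscopy. The documents do not support that:

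- For vital signs, the plan is only "Vital sign measurements will be summarized by treatment group, including changes from baseline at each time point". No abnormality count, shift table or criterion is planned that could be understated.
- For cystoscopy, the rule's parenthesis names only laboratory data and vital signs. Section 11.4.5 counts abnormal cystoscopy by treatment group without a time-point limit.

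The remedy also carries its own ascertainment effect, since subjects drawn more often have more chances to be abnormal.

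**Conclusion.** The point holds for laboratory tests. As Sections 11.4.2 and 11.6.1 are written, an abnormality or peak seen only at an AE-prompted draw is absent from the laboratory summaries supporting a primary safety objective. Each subject so affected is worth 16.7 points in a dose group or 12.5 points in pooled placebo. These are 1/n figures and say nothing about frequency.

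A reader might conclude that such events vanish from the safety analysis altogether. They do not: the prompting AE should be tabulated, the laboratory finding may be, and the value is listed. What the summaries lose is its count as a laboratory abnormality, its size and its shift.

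The conclusion assumes that the SAP adds no worst-value table or exception. Since that text is not in the document supplied, confidence is moderate. This is an inexpensive improvement worth making, and it does not call the design into question.

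**What to change.** Keep unscheduled values out of the by-visit summaries. State in Sections 11.6.1 and 11.4.2, or in the SAP, that two laboratory outputs by treatment group use all post-dose values, scheduled and unscheduled:

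1. The number and percentage of subjects with any post-dose abnormality.
2. A shift table from baseline to the worst post-dose value.

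Add a footnote saying that subjects with more draws have more chances to show an abnormality. No change is needed for vital signs or cystoscopy on this point.

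The cost is one sentence of text and the shells for these two laboratory outputs, with no new data collection. The one drawback is the ascertainment effect that the footnote discloses.
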